3.2 Post Study Access to Therapy

At the end of the study, BMS will not continue to provide BMS supplied study drug to subjects/investigators unless BMS chooses to extend the study. The investigator should ensure that the subject receives appropriate standard of care to treat the condition under study. Pending appropriate preclinical and clinical data to support further drug development, BMS may authorize a study extension, or another mechanism to provide study drug to subjects who received clinical benefit in this study at the discretion of BMS. BMS reserves the right to terminate access to BMS supplied study drug if any of the following occur: a) the marketing application is rejected by responsible health authority; b) the study is terminated due to safety concerns; c) the subject can obtain medication from a government sponsored or private health program; d) BMS terminates development of the drug; or e) therapeutic alternatives become available in the local market.

3.3 Study Population

For entry into the study, the following criteria MUST be met.

3.3.1 Inclusion Criteria

1. Signed Written Informed Consent

- a) Subjects from whom signed written consent for participation in this study has been obtained

2. Target Population

- a) Subjects diagnosed or classified as having moderate to severe pSS (primary Sjögren's syndrome is defined as Sjögren's syndrome in the absence of another autoimmune disease or rheumatologic condition) based on the 2016 ACR-EULAR Classification Criteria (see [Appendix 2](#)) for pSS, with disease duration from time since diagnosis of at least 16 weeks prior to the Screening Visit
- b) ESSDAI \geq 5, including disease activity (any score $>$ 0) in at least one of the following domains: Glandular, Articular, Hematological, Biological, Lymphadenopathy
- c) Positive anti-SS-A/Ro or anti-SS-B/La autoantibody
- d) Unstimulated whole saliva secretion $>$ 0.01 ml/min
- e) Prednisone or other oral corticosteroid use is not required, however, if subject is taking prednisone (or prednisone-equivalent), dose must be tapered to a maximum of 10 mg/day for at least 14 days prior to Day 1 (randomization)
- f) Subject Re-enrollment: This study permits the re-enrollment of a subject that has discontinued the study as a pre-treatment failure (ie, subject has not been randomized / has not been treated). If re-enrolled, the subject must be re-consented

3. Age and Reproductive Status

- a) Males and Females, ages 18 to 70 years old, inclusive, at the time of randomization
- b) Women of childbearing potential (WOCBP) must have a negative serum or urine pregnancy test (minimum sensitivity 25 IU/L or equivalent units of HCG) within 24 hours prior to the start of study drug
- c) Women must not be pregnant or breastfeeding
- d) WOCBP must agree to follow instructions for method(s) of contraception for the duration of treatment with lulizumab or BMS-986142 plus 5 half-lives of the active treatment with the longest half-life given treatment will be blinded (lulizumab [half-life of 7 days]), plus 30 days (duration of ovulatory cycle) for a total of 65 days post treatment completion
- e) Males who are sexually active with WOCBP must agree to follow instructions for method(s) of contraception for the duration of treatment with lulizumab or BMS-986142 plus 5 half-lives of the active treatment with the longest half-life given treatment will be blinded (lulizumab [half-life of 7 days]) for a total of 35 days post-treatment completion. In addition, male subjects must be willing to refrain from sperm donation during this time
- f) Azoospermic males and WOCBP who are continuously not heterosexually active are exempt from contraceptive requirements. However, WOCBP must still undergo pregnancy testing as described in this section

Investigators shall counsel WOCBP and male subjects who are sexually active with WOCBP on the importance of pregnancy prevention and the implications of an unexpected pregnancy. Investigators shall advise WOCBP and male subjects who are sexually active with WOCBP on the use of highly effective methods of contraception (Refer to [Appendix 1](#) for a list of acceptable methods), which have a failure rate of < 1% when used consistently and correctly.

3.3.2 Exclusion Criteria

1. Target Disease Exceptions

- a) Secondary Sjögren's syndrome
- b) Other systemic autoimmune disease (eg, RA, SLE, multiple sclerosis [MS], vasculitis)
- c) Subjects with a condition that, in the opinion of the Investigator, may confound the diagnosis of pSS, including but not limited to: head and neck radiation, graft versus host disease, lymphoma, prior or current diagnosis of sarcoidosis, chronic viral diseases such as HIV, HTLV, or HCV, or IgG4 disease
- d) Very severe pSS or severe complications of pSS at the time of the screening visit, including but not limited to:
 - i) severe or ESSDAI Renal Domain High Activity - renal disease including but not limited to interstitial nephritis, glomerulonephritis, nephrotic syndrome with proteinuria > 3 gm/day and/or serum creatinine \geq 2.0 mg/dL
 - ii) severe or ESSDAI CNS or PNS Domain High Activity - neurologic disease including but not limited to central or peripheral neuropathy or CNS vasculitis
 - iii) severe or ESSDAI Pulmonary Domain High Activity - pulmonary disease including but not limited to interstitial pneumonitis or obstructive bronchiolitis
 - iv) severe or ESSDAI Cutaneous Domain High Activity - documented vasculitis (mild isolated cutaneous vasculitis is not a contraindication)
 - v) lymphoma or other lymphoproliferative disease
 - vi) cryoglobulinemia with neurological, renal or visceral involvement
 - vii) severe or ESSDAI Muscular Domain High Activity - myositis
 - viii) any complication requiring corticosteroid therapy \geq 1 mg/kg during the 30 days preceding the screening visit
- e) Subjects with an acutely infected salivary gland within 30 days of the screening visit

2. Medical History and Concurrent Diseases

- a) Subjects at risk for tuberculosis (TB). Specifically, subjects with:
 - i) Current clinical, radiographic or laboratory evidence of active TB
 - ii) A history of active TB within the last 3 years, even if treated
 - iii) A history of active TB greater than 3 years ago unless there is documentation that the prior anti-TB treatment was appropriate in duration and type

- iv) Therapy for latent TB which has not been completed as per local country guidelines
- v) Positive interferon gamma release assay (IGRA) for TB unless proper treatment is documented as above
- b) Subjects with any bacterial infection within the last 60 days prior to screening (enrollment), unless treated and resolved with antibiotics, or any chronic or history of recurrent bacterial infection (such as chronic pyelonephritis, osteomyelitis and bronchiectasis)
- c) Subjects who have a history of systemic fungal infections (such as histoplasmosis, blastomycosis, or coccidioidomycosis)
- d) Subjects with history of recurrent herpes zoster (more than 1 episode) or disseminated (more than 1 dermatome) herpes zoster or disseminated herpes simplex, or ophthalmic zoster will be excluded. Symptoms of herpes zoster or herpes simplex must have resolved more than 60 days prior to screening visit (enrollment)
- e) Subjects with evidence (as assessed by the investigator) of active or latent bacterial or viral infection at the time of potential enrollment, including subjects with history or evidence of Human Immunodeficiency Virus (HIV) infection or who have a positive HIV test at screening
- f) Any significant concurrent medical condition at the time of screening or baseline visit, including, but not limited to, the following:
 - i) Any major illness/condition or evidence of an unstable clinical condition (eg, renal, hepatic, hematologic, gastrointestinal, endocrine, pulmonary or active infection/infectious illness) that, in the Investigator's judgment will substantially increase the risk to the subject if he or she participates in the study
 - ii) Cancer or lymphoproliferative disease within the previous 5 years (other than resected cutaneous basal cell or squamous cell carcinoma that has been treated with no evidence of recurrence). Subjects with a history of lymphoma at any time are excluded
 - iii) Female subjects with a breast cancer screening suspicious for malignancy, and in whom the possibility of malignancy cannot be reasonably excluded following additional clinical, laboratory or other diagnostic evaluations
 - iv) Class III or IV congestive heart failure as defined by the New York Heart Association
 - v) Acute coronary syndrome (eg, myocardial infarction, unstable angina pectoris) and/or any history of significant cerebrovascular disease within 24 weeks before screening
 - vi) Liver cirrhosis or other underlying liver disease (eg, non-alcoholic steatohepatitis, primary sclerosing cholangitis, primary biliary cirrhosis/cholangitis)
 - vii) Any significant coagulation or platelet function disorders (eg, von Willebrand's disease)
 - viii) Any gastrointestinal condition that could impact study drug absorption
 - ix) Any other concomitant medical conditions that, in the opinion of the investigator, might place the subject at unacceptable risk for participation in this study

- g) Major surgical intervention or scheduled surgery during the 8 weeks preceding enrollment
- h) Subjects currently on hydroxychloroquine who cannot provide documentation of an ophthalmologic evaluation (including evaluation of the retina) or who have evidence of retinopathy within 6 months of screening
- i) Donation of blood to a blood bank or in a clinical study (except a screening visit) within 4 weeks of study drug administration (within 2 weeks for plasma only)
- j) Blood transfusion within 4 weeks of study drug administration
- k) Inability to be venipunctured and/or tolerate venous access
- l) Subjects with a history of (within 12 months of signing the consent), or known current problems with drug or alcohol abuse
- m) Subjects with a history or suspicion of unreliability, poor cooperation, or non-compliance with medical treatment
- n) Subjects who have received treatment with an investigational drug within 12 weeks or less than 5 terminal half-lives of elimination (whichever is longer) of randomization (Day 1)
- o) Live vaccine administration to subjects within 30 days of enrollment, during the screening or study periods, or for 8 weeks after completion of dosing
- p) Subjects who are unwilling or have difficulty swallowing oral tablets

3. Physical and Laboratory Test Findings

- a) Subjects with positive HBsAg, or subjects with positive anti-HBc antibody with detectable quantitative HBV DNA. Subjects with negative HBsAg but with high risk for latent HBV infection (including subjects with known family history of HBV infection, HBV carrier, personal medical history of hepatitis or blood transfusion history) should be tested for quantitative HBV DNA at the investigator's discretion. Subjects with positive quantitative HBV DNA are excluded from the study
- b) Hepatitis C antibody-positive subjects who are also HCV positive by confirmatory testing such as PCR
- c) Positive HIV test
- d) Have any clinically significant laboratory abnormalities (confirmed by repeat testing) including but not limited to:
 - i) Hepatic
 - (1) ALT $\geq 2 \times$ ULN (Upper limit of normal)
 - (2) AST $\geq 2 \times$ ULN
 - (3) Total bilirubin $\geq 1.5 \times$ ULN
 - ii) Hematology
 - (1) WBC count $< 3000/\text{mm}^3$ ($3.0 \times 10^9/\text{L}$)

- (2) Hemoglobin < 9 g/dL
- (3) Absolute neutrophil count < 1000/mm³ (1.0 x 10⁹/L)
- (4) Platelets < 100,000/mm³ (100 x 10⁹/L)
- iii) Creatinine ≥ 2.0 mg/dL
- e) Subjects with a positive TB IGRA (such as Quantiferon® TB Gold, Refer to [Section 3.3.2 #2a](#))
- f) Any other significant laboratory abnormalities that, in the opinion of the Investigator, might place the subject at unacceptable risk for participation in this study (please discuss with BMS Medical Monitor if there are any questions in regards to inclusion/exclusion criteria)

4. Allergies and Adverse Drug Reaction

- a) History of any significant drug allergy (such as anaphylaxis or hepatotoxicity)

5. Prior and Concomitant Medications

- a) Oral corticosteroids > 10 mg/day within 14 days of dosing (Day 1), or corticosteroid therapy ≥ 1 mg/kg during the 4 weeks preceding enrollment
- b) Intravenous, intramuscular or intra-articular corticosteroids within 4 weeks of enrollment
- c) Treatment started or an unstable dose of non-steroidal anti-inflammatory drugs (NSAIDs), pilocarpine, cevimeline (Evoxac®), topical corticosteroid eye preparations, lifitegrast (Xiidra®), autologous serum eye drops, or cyclosporine eye drops (Restasis®) within 14 days of dosing (doses must be held for at least 12 hours prior to any study visit after Screening)
- d) Use of methotrexate, cyclophosphamide, cyclosporine, tacrolimus, azathioprine, mycophenolate mofetil (MMF) or leflunomide within 12 weeks of enrollment
- e) Treatment started or an unstable dose of hydroxychloroquine (Plaquenil®) within 8 weeks of enrollment. Doses higher than 400 mg/day are not permitted. Use of other antimalarials (eg, chloroquine, quinacrine) is not permitted
- f) Use of rituximab within 6 months prior to enrollment or lack of recovery of CD19+ B cells to > 10/μl at screening in any subject with prior rituximab use
- g) Previous treatment with other biologics either marketed or in development (eg, abatacept, tocilizumab, belimumab, TNF inhibitors) within 6 months prior to enrollment
- h) Subjects are not permitted to have new installation of lacrimal punctum plugs within 4 weeks of randomization (Day 1) or during the course of the study. Subjects with existing lacrimal punctum plugs are permitted to enroll, and have these plugs replaced as necessary during the study

6. Other Exclusion Criteria

- a) Prisoners or subjects who are involuntarily incarcerated. (Note: under certain specific circumstances a person who has been imprisoned may be included or permitted to continue as a subject. Strict conditions apply and Bristol-Myers Squibb approval is required)

- b) Subjects who are compulsorily detained for treatment of either a psychiatric or physical (eg, infectious disease) illness
- c) Inability to comply with restrictions and prohibited treatments as listed in Section 3.4
- d) Adults under guardianship or protection
- e) Participation in another interventional therapeutic trial (treatment underway or in study follow-up period)

Eligibility criteria for this study have been carefully considered to ensure the safety of the study subjects and that the results of the study can be used. It is imperative that subjects fully meet all eligibility criteria.

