7.2 Study Conduct

Relevant protocol deviations, which could have an impact on the primary/key efficacy endpoint, will be identified for all subjects who are randomized and receive study medication during the double-blind period. Details of relevant protocol deviations are provided in [APPENDIX 1](#).

All subjects with relevant protocol deviations that could affect the primary efficacy will be identified prior to database lock and unblinding of treatment assignment. All relevant protocol deviations will be listed and summarized by treatment group. The subjects identified with relevant protocol deviation will not be excluded from any analysis population described in [Section 6.3](#). If at least 10% of total subjects in all treatment arms in the efficacy analysis population demonstrate relevant protocol deviations, a per-protocol analysis may be performed. The per-protocol analysis will exclude data from subjects with relevant protocol deviations as specified in APPENDIX 1.

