APPENDIX 1 RELEVANT PROTOCOL DEVIATIONS

Number	Relevant Protocol Deviation Criteria	Exclusion Level
1	Randomized subjects who do not have moderate to severe primary Sjögren's syndrome, defined as Sjögren's syndrome in the absence of another autoimmune disease or rheumatologic condition) based on the 2015 ACR-EULAR Classification Criteria.	Complete exclusion
2	Randomized subjects without ESSDAI \geq 5, including disease activity (any score $>$ 0) in at least one of the following domains: Glandular, Articular, Hematological, Biological, Lymphadenopathy.	Complete exclusion
3	Randomized subjects without Positive anti-SS-A/Ro or anti-SS-B/La autoantibody.	Complete exclusion
4	Randomized subjects who received more than 10mg/day of prednisone (or prednisone equivalent) for at least 14 days prior to Day 1 (randomization).	Complete exclusion
5	Randomized subjects who did not receive at least 4 consecutive doses of Lulizumab or matching placebo.	Partial exclusion (Efficacy data after the 21th day of the interruption will be excluded)
6	Randomized subjects who did not receive BMS-986142 or matching placebo for at least 14 consecutive days.	Partial exclusion (Efficacy data after the 14th day of the interruption will be excluded)
7	Randomized subjects to placebo receiving active medication dose of Lulizumab for at least 4 doses and BMS-986142 for at least 14 doses.	Partial exclusion (Efficacy data from the first dose date of active medication will be excluded)
8	Randomized subjects receiving initiating or increasing the baseline dose (if already in such a medication) in any of the protocol specified list of restricted and prohibited treatments during double-blind treatment period.	Partial exclusion (Efficacy data from the first dose date of restricted or protocol medication will be excluded)
9	Randomized subjects less than 80% or more than 120% compliant with any of the double-blind treatment regimens.	Complete exclusion

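### The per-protocol deviation list omits all prior-medication windows except oral prednisone, and its on-treatment row does not clearly catch a prohibited drug continued unchanged

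*Protocol*

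**What the plan says.** Protocol 3.3.2 sets several medication windows before entry. Exclusion 5(d) bars "Use of methotrexate, cyclophosphamide, cyclosporine, tacrolimus, azathioprine, mycophenolate mofetil (MMF) or leflunomide within 12 weeks of enrollment". Exclusion 5(f) bars "Use of rituximab within 6 months prior to enrollment or lack of recovery of CD19+ B cells" above a stated count. Exclusion 5(g) bars "Previous treatment with other biologics either marketed or in development" within 6 months, and 5(b) bars "Intravenous, intramuscular or intra-articular corticosteroids within 4 weeks of enrollment". Exclusion 2(n) bars "Subjects who have received treatment with an investigational drug within 12 weeks or less than 5 terminal half-lives of elimination", whichever is longer. The second clause of 5(a) bars corticosteroids at 1 mg/kg or more in the previous 4 weeks, and 5(e) bars new or unstable hydroxychloroquine within 8 weeks. Protocol 3.4.1.2 (Immunosuppressives) prohibits the conventional agents, biologics and other investigational drugs through screening, dosing and follow-up.

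SAP 7.2 describes its subject as "Relevant protocol deviations, which could have an impact on the primary/key efficacy endpoint". These deviations are to be identified before database lock and unblinding, then listed and summarised by arm. The per-protocol analysis drops data only for the deviations in Appendix 1.

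Appendix 1 has nine rows. Rows 1 to 4 remove certain eligibility breaches completely, and row 4 (oral prednisone above 10 mg/day) is the only one on medication before Day 1. Row 8 deals with restricted and prohibited treatments during the double-blind period. It begins "Randomized subjects receiving initiating or increasing the baseline dose (if already in such a medication" and excludes efficacy data from the first dose of the drug.

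**The concern.** The per-protocol repeat is the planned check that the primary result does not depend on protocol breaches. SAP 7.2 defines relevance by possible effect on the primary endpoint. Recent rituximab, another biologic, an immunosuppressant or an injected steroid fits that definition at least as well as oral prednisone does.

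The list is uneven. A subject on 12 mg/day of prednisone for the 14 days before Day 1 is removed completely. A subject given rituximab one month before enrolment is kept.

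Three things follow. The breaches stay in the per-protocol data. They are missing from the deviation summary by arm, even if no per-protocol analysis is run. And they do not count toward the threshold that decides whether it is run.

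**Working it through.** **Step 1: medication windows against Appendix 1.**

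| Protocol exclusion | Agent and window | Appendix 1 row |
|---|---|---|
| 5(a), first clause | oral steroid above 10 mg/day, 14 days | 4 |
| 5(a), second clause | steroid at 1 mg/kg or more, 4 weeks | none |
| 5(b) | injected steroids, 4 weeks | none |
| 5(c) | NSAIDs, secretagogues, eye preparations, 14 days | none |
| 5(d) | conventional immunosuppressants, 12 weeks | none |
| 5(e) | hydroxychloroquine stability, 8 weeks | none |
| 5(f) | rituximab, 6 months or no CD19+ recovery | none |
| 5(g) | other biologics, 6 months | none |
| 2(n) | investigational drugs, 12 weeks or 5 half-lives | none |

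Row 4 is itself narrow. Read literally, it needs 14 days or more above 10 mg/day, whereas 5(a) bars any such dose within 14 days of dosing.

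**Step 2: row 8.** It is confined to the double-blind period, so it cannot reach a drug stopped before Day 1. For a drug already being taken, its parenthesis ties the trigger to a dose increase. A prohibited drug continued at an unchanged dose is therefore not clearly caught, although protocol 3.4.1.2 prohibits it throughout.

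**Step 3: the triggers.**

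- SAP 7.2: at least 10% of all subjects, and the analysis is optional. 0.10 × 75 = 7.5, so 8 subjects. At the maximum size, 0.10 × 120 = 12.
- SAP 7.5.1: more than 10% of any arm with a deviation that excludes efficacy data, and the analysis is mandatory. 0.10 × 25 = 2.5, so 3 subjects. With 40 per arm, 0.10 × 40 = 4, so 5.

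The two rules can disagree. Three deviators in one arm and none elsewhere meet 7.5.1 (3/25 = 12%) but not 7.2 (3/75 = 4%). With 120 subjects, four in each arm meet 7.2 (12/120 = 10%) but not 7.5.1 (4/40 is exactly 10%).

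One uncounted breach can matter. An arm of 25 with two listed deviators is at 2/25 = 8%, and counting one washout breach makes it 3/25 = 12%.

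**Step 4: would other outputs show these breaches?** Protocol 8.2 defines enrolment as signing consent, so most of the windows look back from consent. SAP 7.3.4 counts a drug as prior medication only if at least one dose was taken on or after the day of consent. A drug stopped inside its window but before consent is a breach that this summary omits. SAP 7.4.5 covers corticosteroids, NSAIDs and non-biologic DMARDs, but not biologics.

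**Step 5: cost of removing more subjects.** The protocol's power figure reproduces. For a two-sided two-sample t-test at 0.05 with difference 3 and SD 3.2, the noncentrality is 3 / (3.2 × √(2/n)) on 2n − 2 degrees of freedom. At n = 25 this is 3.31, giving 90.1% against the stated approximate 90%. Losing 1, 2 or 3 subjects per arm gives 88.9%, 87.5% or 85.9%.

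**The case against.** **Small consequence.** Efficacy is analysed on the MITT population, which keeps all deviators. Only a conditional sensitivity analysis is affected, and only if ineligible subjects are randomised despite checks at screening and Day 1. A sponsor may also choose which deviations count as relevant. The point about size stands. The point about choice is weaker, because rows 1 to 4 already remove eligibility breaches completely and the documents give no reason for stopping at oral prednisone.

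**Row 8 may already cover continuing use.** Its wording is garbled, and one reading takes in any receipt. A reader might infer that a subject continuing methotrexate unchanged certainly meets no criterion. The text does not support that certainty. The parenthesis favours the narrow reading but does not settle it. Such a subject could also be removed under another row, such as compliance.

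**Continuing users must stop study drug.** Protocol 3.5 requires this on use of prohibited medication. SAP 8.3 then leaves out efficacy data later than 28 days after the last injection or 2 days after the last oral dose, whichever is later. This limits later data from detected users. It does not remove their earlier data, and it does not deal with the residual effect of a drug stopped before entry.

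**A numerical shift is tempting.** A reader might assign each violator an assumed 3 to 6 extra ESSDAI points, moving an arm mean by 3/25 = 0.12 to 6/25 = 0.24. Nothing in the documents supports that range. A drug continued unchanged from baseline is already reflected in the baseline score, and a waning earlier drug could act in the opposite direction. Breaches before Day 1 also precede randomisation, so they are balanced across arms in expectation.

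**Conclusion.** The gap holds on the text. Subjects randomised in breach of 5(a) second clause, 5(b), 5(d), 5(e), 5(f), 5(g) or 2(n) stay in the per-protocol repeat, unless another row happens to catch them. Those breaches do not count toward the 8 of 75 or 3 of 25 triggers. For prohibited drugs continued unchanged, the defect is an unclear rule rather than a proven omission.

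A reader might go further and infer that the primary result is at risk. It is not: the MITT analysis does not use this list. The number of such breaches and the direction of any effect are unknown, and no ESSDAI shift can be derived. The conclusion rests on reading Appendix 1 as the complete list, which is how SAP 7.2 uses it. It is a cheap and worthwhile correction to a sensitivity analysis.

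**What to change.** Make these changes before database lock and unblinding:

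- **Appendix 1.** Add complete-exclusion rows for randomised subjects who breach 5(a) second clause, 5(b), 5(d), 5(e), 5(f), 5(g) or 2(n). Exclusion 5(c) also has no row; the sponsor should say whether that is intended.
- **Row 8, part (i).** Starting or increasing a permitted stable-dose drug keeps the present partial exclusion. Nothing that the row catches now should be lost.
- **Row 8, part (ii).** Any receipt of a drug on the Immunosuppressives list in protocol 3.4.1.2, including biologics and other investigational drugs, is a deviation. If use continues from before Day 1, exclusion is complete; otherwise it runs from the first on-study dose. Limit this part to that list. Section 3.4.1.2 also prohibits hormonal contraceptives and estrogen replacement, on grounds that the documents do not link to ESSDAI.
- **Triggers.** Count these deviations, and reconcile SAP 7.2 with 7.5.1 on denominator, threshold and whether the analysis is optional.

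The cost is SAP wording, programming and a slightly smaller per-protocol set. SAP 8.5 says start and stop dates of all non-study medications are collected, but the sponsor should confirm that the CRF captures drugs stopped before consent, since the SAP 7.3.4 definition leaves them out. The MITT analysis and trial conduct do not change.
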